Objective	
Primary:
 
-To assess the impact of complement activation on platelet count.
 
Secondary:
 
- To assess the specific pathway of complement activation, mtDNA levels and their effects on platelet count and platelet function using mean platelet volume to platelet count ratio (MPV/PTC) and specific platelet function by fluorescence-activated cell sorting (FACS).
 
- To explore whether these variables correlate with transfusion requirements, postoperative morbidity (need for revision surgery, cardiovascular events including thromboembolic events, sepsis, single or multiple organ failure according to SOFA Score) and in hospital mortality.

Endpoints and Evaluation Parameters	
Primary endpoint:
 
- Correlation of the change of C5b-9 and change of platelet count from baseline (T0) to after 15 minutes of administration of protamine (T2).
 
Secondary endpoints:
 
- correlation between levels of complement factors [c5b-9, C1q (C1r/C1s), C3a, C5a, MBL, Factor B, Factor D], mtDNA level [human NADH dehydrogenase 1 gene] and platelet function [MPV/PTC ratio and FACS for platelet activation factor 4 (PAF-4)]
 
- correlation between levels of complement [see above] and concentration of coagulation factors [F I – F XIII, FXa, FXIIa, Kallikrein, Bradykinin, endogenous thrombin potential (ETP)] and transfusion requirements
 
- correlation of levels of complement, mtDNA and platelet function to postoperative morbidity (need for revision surgery, cardiovascular events including thromboembolic events, sepsis, single or multiple organ failure according to SOFA Score) and in hospital mortality

Number of Patients	190

Duration of Patient Participation	- day of surgery to postoperative day three (POD 3) - Follow-Up Period "Medical Monitoring": until discharge or day 30
Dates of Beginning and End of Study	Date of beginning of study: 1.July 2018 Date of end of study: 1.July 2020
Inclusion Criteria	I.1. Male and female subjects \geq 18 years and \leq 85 years I.2. elective coronary artery bypass graft surgery on cardiopulmonary bypass (CPB) with or without valve surgery (max. 2 valves) and elective valve surgery (max. 2 valves) I.3. ASA I - IV I.4. written informed consent
Exclusion Criteria	E.1. emergency CABG with cardiac valve surgery and emergency valve surgery and emergency aortic dissection E.2. preexisting complement deficiency syndromes E.3. preexisting thrombocytopathy or thrombocytopenia (platelet count below 100 G/L) E.4. Known history of congenital coagulopathy E.5. Patients that are known to be pregnant E.6. Known participation in another interventional clinical trial
Study-related Measurements and Data collection	Study related measurements: complement factors, platelet function (FACS), mtDNA, concentrations of coagulation factors and thrombin generation will be obtained at baseline (T0) and at several time points (T1-T8) during and after CABG until POD3. Data collection: Details on patient's condition before surgery, as well as all clinical data until discharge or day 30
Study Procedure	Except study related blood sampling patient's care is not influenced by the study and follows clinical routine. The Visit time points are: T0 baseline: after insertion of arterial cannula beginning surgery T1 after re-opening aortic clamp on CPB T2 15 minutes after protamine infusion T3 end of surgery = admission lab at the postoperative intensive care unit T4 4 hours after end of surgery T5 12 hours after end of surgery T6 24 hours after surgery begin T7 48 hours after surgery begin T8 72 hours after surgery begin T9 30 days after surgery or hospital admission Study related blood sampling (T0-T8): 
▪ Levels of complement factors: c5-b9, C1q (C1r/C1s), C3a, C5a, MBL, Factor B, Factor D

	
 ▪ mtDNA (human NADH dehydrogenase 1 gene) ▪ Platelet count, mean platelet volume, fluorescence-activated cell sorting (FACS) ▪ Coagulation factors: FI – FXIII, FXa, FXIIa, Kallikrein, Bradykinin, endogenous thrombin potential (ETP) 
Routine laboratory blood sampling (T0-T9):
 
activated clotting time (ACT), Rotem parameters, Multiplate test analysis, whole blood cell count, standard plasmatic coagulation tests, blood gas analysis, CRP, Procalcitonin (PCT), renal and liver function parameters, cardiac enzymes (CK, CK-MB, Myoglobin, Trop T, NTpro BNP)
 
Clinical Data:
 
The following parameters will be collected at baseline(T0):
 
age, gender, body weight(kg) and size (cm), medical history (chronic renal impairment, Diabetes, Hypertension, previous myocardial infarction, previous stroke, previous percutaneous coronary intervention, previous CABG), pre-medication, Euroscore II.
 
During surgery and until POD 3 following data will be collected if available:
 
Details on CPB, Cell Saver blood volume, blood pressure (BP), hear rate (HR), central venous pressure (CVP), mean pulmonary artery pressure (MPAP),cardiac index (C.I.), cardiac output (C.O.), Oxygen Saturation (SpO2), Horowitz, Fraction of inspired Oxygen (FiO2), Diuresis per hour, Concomitant Medication, transfusion and coagulation products, need for haemofiltration , need for extracorporeal membrane oxygenation (ECMO) and/or need for inhalative NO.

Risk-Benefit Analysis	There is no risk for pain and infection since the blood is drawn from a routinely done cannula. The total amount of blood sampling is 150 ml within 3 days and will not harm the patients. The patients benefit from the intensified diagnostics.
Statistics	Primary endpoint: Correlation of the change of C5b-9 and change of platelet count from baseline (T0) to after 15 minutes of administration of protamine (T2).

STUDY FLOW CHART

	T0 Baseline Day of surgery Day 0	T1 CPB Opening Aortic crossclamp Day0	T2 CPB 15min after Protamin Day0	T3 End of surgery Admission post Op ICU Day0	T4 PACU 4h post surgery Day 0	T5 PACU 12h post surgery Day 0	T6 PACU 08:00 Day1	T7 ICU 08:00 Day2	T8 ICU 08:00 Day3	T9 Ward/ICU Day 30
Special laboratory ¹	x	x	x	x	x	x	x	x	x	
Routine laboratory ²	x	x	x	x	x	x	x	x	x	x
Clinical data ³	x	x	x	x	x	x	x	x	x	x
Concomitant Medication	x	x	x	x	x	x	x	x	x	
Transfusions/ Coagulation products		x	x	x	x	x	x	x	x	
Scores	Euroscore II				SOFA*	SOFA*	SOFA*	SOFA*	SOFA*	
Final survey										x

*calculation of SOFA if patient stays at ICU

¹ c5-b9, C1q (C1r/C1s), C3a, C5a, MBL, Factor B, Factor D, mtDNA, Platelet count, mean platelet volume, fluorescence-activated cell sorting (FACS), FI – FXIII, FXa, FXIIa, Kallikrein, Bradykinin, endogenous thrombin potential (ETP)

² activated clotting time (ACT), Rotem parameters, Multiplate test analysis, whole blood cell count, standard plasmatic coagulation tests, blood gas analysis, CRP, Procalcitonin (PCT), renal and liver function parameters, cardiac enzymes (CK, CK-MB, Myoglobin, Trop T, NTpro BNP)

³ age, gender, body weight(kg) and size (cm), medical history (chronic renal impairment, Diabetes, Hypertension, previous myocardial infarction, previous stroke, previous percutaneous coronary intervention, previous CABG), pre-medication, Euroscore II, Details on CPB, Cell Saver blood volume, blood pressure (BP), hear rate (HR), central venous pressure (CVP), mean pulmonary artery pressure (MPAP),cardiac index (C.I.), cardiac output (C.O.), Oxygen Saturation (SpO2), Horowitz, Fraction of inspired Oxygen (FiO2), Diuresis per hour, Concomitant Medication, transfusion and coagulation products, , need for extracorporeal membrane oxygenation (ECMO) and/or need for inhalative NO.

ABBREVIATIONS

ASA	American Society of Anesthesiologists (ASA) Score is a global score that assesses the physical status of patients before surgery.
BGA	Blood gas analysis
CA	Competent Authority
CABG	Coronary Artery Bypass Graft
CPB	Cardiopulmonary Bypass
CRF	Case Report Form
ECMO	extracorporeal membrane oxygenation
ETP	endogenous thrombin potential
FI - FXIII	coagulation factor I - XIII
FACS	fluorescence-activated cell sorting
GCP	Good Clinical Practice
ICH	International Conference on Harmonization
ICU	Intensive Care Unit
mtDNA	mitochondrial DNA
MPV	mean platelet volume
MPV ratio	Mean platelet volume/mean platelet count
NA	not applicable
ND	not done
POD	postoperative day
RIFLE Score	Risk Injury Failure Loss Endstage kidney injury score
SOFA Score	sequential organ failure assessment score

PLATELETS AFTER COMPLEMENT ACTIVATION IN CARDIAC SURGERY - PAC

1. INTRODUCTION

1.1. Background

Patients undergoing coronary artery bypass graft surgery (CABG) frequently exhibit postoperative bleeding complications which are still a major cause for morbidity and mortality (1). One major contributing factor is the loss of platelets and impaired platelet function. During cardiopulmonary bypass (CPB) blood comes in close contact with foreign surfaces which induces a series of reactions; especially the complement system as part of the innate immunity is highly activated (2). Due to the strong crosslink between complement system, platelet function and the plasmatic coagulation it is likely that complement activation during CPB has an impact on the overall process of clot formation. (3). Besides the activation of the complement system there is growing evidence that the occurrence of mitochondrial DNA (mtDNA) during CPB might be related to further platelet activation (4). Activated platelets may enhance micro-thrombosis leading to organ failure and thereby contributing to postoperative morbidity.

Several studies investigated the effect of complement activation in cardiac surgery patients (2;5;6-7) however, it is still unclear whether the activation of the complement system further increases platelet loss.

1.2. Need for the Study

One major complication during and after CABG surgery is bleeding requiring transfusion and even reoperation in about 2%- 8% of patients.

A recent study shows that impaired hemostasis was observed in 9,5 - 21,5% of these cases (1). As bleeding complications increase patient morbidity and mortality, this study is designed to investigate, the possible mechanisms of platelet loss during CABG.

We hypothesize that increased complement activation during CPB leads to platelet activation and loss of platelets. We further hypothesize that the degree of complement activation and levels of mtDNA correlate with postoperative bleeding, transfusion requirements and clinical outcome.

1.3. Risk Benefit analysis

For blood withdrawal no additional arterial/venous puncture is needed.

Blood samples will all be withdrawn from preexisting arterial cannulas. Only if there is no arterial line available, blood will be withdrawn of an also preexisting central venous catheter.

The total amount of blood collected over the entire study period will be 150 ml, which seems to be a negligible risk compared to the average blood loss in CABG surgery.

The findings of this study will help to understand further details of the mechanism of platelet drop and complement activation during and after CABG surgery. Furthermore, the results could help to develop new therapeutic strategies to avoid activation of the complement and hemostatic systems during CPB which may decrease bleeding complications in CABG patients.

2. STUDY OBJECTIVES

2.1. Primary Study Objective

The aim of the study is to examine the correlation between complement activation (c5b-9) and platelet decline during elective coronary artery bypass graft (CABG) **with or without valve surgery (max. 2 valves) and elective valve surgery (max. 2 valves)** on cardiopulmonary bypass (CPB).

2.2. Further Study Objectives

A secondary aim of the study is to investigate the specific pathway of complement activation, the mtDNA levels and the interaction with platelet function.

Therefore we search for correlations between levels of complement factors [c5b-9, C1q (C1r/C1s), C3a, C5a, MBL, Factor B, Factor D], mtDNA level [human NADH dehydrogenase 1 gene] and platelet function [MPV/PTC ratio and FACS for platelet activation factor 4 (PFA)].

Further it will be explored whether the level of complement activation and levels of mtDNA and the plasmatic coagulation system correlate with transfusion requirements, postoperative morbidity (need for revision surgery, cardiovascular events including thromboembolic events, sepsis, single or multiple organ failure according to SOFA Score), and in hospital mortality.

We will correlate levels of complement [see above] and concentration of coagulation factors [F I – F XIII, FXa, FXIIa, Kallikrein, Bradykinin, endogenous thrombin potential (ETP)] and transfusion requirements and correlate levels of complement, mtDNA and platelet function to postoperative morbidity (need for revision surgery, cardiovascular events including thromboembolic events, sepsis, single or multiple organ failure according to SOFA Score) and in hospital mortality.

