3.3. Blood sampling

3.3.1 Study related blood samples (T0-T8)

- Levels of complement factors: c5-b9, C1q (C1r/C1s), C3a, C5a, MBL, Factor B, Factor D
- mtDNA (human NADH dehydrogenase 1 gene)
- Platelet count, mean platelet volume, fluorescence-activated cell sorting (FACS)
- Coagulation factors: FI – FXIII, FXa, FXIIa, Kallikrein, Bradykinin, endogenous thrombin potential (ETP)
- Residual plasma and serum from blood samples will be stored at -80°C for further differentiated complement and mtDNA assays if useful

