3.4. Primary Study Endpoint

The primary endpoint is the correlation of the change of C5b-9 and change of platelet count from baseline (T0) to after 15 minutes of administration of protamine (T2).

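### MPV/PTC is labelled platelet function, but platelet count is its denominator, so a marker related only to count will look related to function

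*Protocol*

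**What the plan says.** - **Synopsis, Objective.** The secondary objective covers "effects on platelet count and platelet function using mean platelet volume to platelet count ratio (MPV/PTC") "and specific platelet function by fluorescence-activated cell sorting (FACS"). Count and function are named as two targets, the ratio is attached to the first phrase, and FACS is the specific function measure.
- **Synopsis, secondary endpoints.** Complement and mtDNA levels are correlated with "platelet function [MPV/PTC ratio and FACS for platelet activation factor 4 (PAF-4").
- **Section 2.2.** The same grouping appears among the objectives: "platelet function [MPV/PTC ratio and FACS for platelet activation factor 4 (PFA"). Platelet function is then also correlated with postoperative morbidity and in-hospital mortality.
- **Abbreviations.** The MPV ratio is defined as "Mean platelet volume/mean platelet count".
- **Section 1.2.** The hypothesis is that complement activation "leads to platelet activation and loss of platelets".
- **Section 3.5.** Platelet function is listed with FACS as the only method; the ratio is absent.
- **Section 3.3.1.** The T0-T8 study samples include "Platelet count, mean platelet volume, fluorescence-activated cell sorting (FACS").
- **Section 7, Sample size estimation.** The ratio from the cited CABG study stands for platelets, and its correlation with mtDNA is used to predict a correlation with the change of platelets.

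**The concern.** The ratio rises when platelets are lost, even if MPV does not move. Section 1.2 hypothesises both activation and loss, and a measure that responds to loss alone cannot tell them apart. If a complement factor or mtDNA level tracks the concurrent count and nothing else, its correlation with MPV/PTC could be reported as an effect on function. In the other direction, a marker that truly relates to MPV is diluted, because count usually contributes most of the spread of the ratio.

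At stake is the reading of a secondary objective that names count and function separately. A correlation with the ratio would not show which of them is involved. If the ratio represents function in the analyses of morbidity and mortality, the same ambiguity follows there.

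**Working it through.** **Inputs from the protocol.** The ratio is MPV divided by platelet count (Abbreviations). Levels, not changes, are correlated (Section 2.2). The evaluable sample is 162 (Section 7). The protocol gives no figure for the ratio problem itself. Its 162 reproduces: ((1.960 + 1.645) / (atanh 0.683 − atanh 0.5))² + 3 = (3.605 / 0.2854)² + 3 = 162.5.

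**Assumed inputs.** The protocol gives no spread for MPV or count. The grid is log-SD of MPV (sM) 0.06, 0.10, 0.15; log-SD of count (sC) 0.20, 0.30, 0.40; MPV-count correlation ρ −0.4, −0.2, 0, +0.2, +0.4. That is 3 × 3 × 5 = 45 cells. The central case is 0.10 / 0.30 / 0. The marker-count Spearman correlation is set at 0.3 in size.

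**Step 1: how closely the ratio follows count.** Since log ratio = log MPV − log count,

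k = corr(log ratio, log count) = (ρ·sM − sC) / √(sM² + sC² − 2ρ·sM·sC).

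| sM / sC / ρ | k |
|---|---|
| 0.10 / 0.30 / 0 | −0.30 / √0.10 = −0.949 |
| 0.15 / 0.20 / +0.4 (weakest) | −0.14 / √0.0385 = −0.714 |
| 0.06 / 0.40 / −0.4 (strongest) | −0.424 / √0.1828 = −0.992 |

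**Step 2: what a count-only marker passes on.** If the marker is independent of MPV given count, corr(marker, ratio) = k × corr(marker, count). Conversion to Spearman uses (6/π)·asin(r/2). A Spearman of 0.3 is a Pearson of 2·sin(π × 0.3 / 6) = 0.3129. In the central case 0.949 × 0.3129 = 0.297, which converts back to 0.284. The share carried is 0.95; over the grid it runs from 0.71 to 0.99.

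A wider range (CVs of 15-40% for count and 5-15% for MPV, ρ −0.5 to +0.3) gives a lowest share of 0.59, at equal CVs of 15% and ρ = +0.3.

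**Step 3: simulated studies of 162 patients, two-sided p < 0.05, count-only marker at 0.3.**

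| Analysis | Central | Grid |
|---|---|---|
| Spearman, marker with ratio | 0.28 | 0.21 to 0.30 |
| Ratio nominally significant | 96% | 78% to 97% |
| Partial Spearman given count, significant | about 5% | 5% to 6% |

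The last row follows from the count-only set-up. It shows only that conditioning on count removes the count route. In the 0.59 case of the wider range the ratio shows 0.17 and is significant in 61% of studies.

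**Step 4: the converse.** For a marker tied only to MPV, corr(log ratio, log MPV) = (sM − ρ·sC) / √(sM² + sC² − 2ρ·sM·sC). In the central case this is 0.10 / √0.10 = 0.316, so a Spearman of 0.3 with MPV becomes 0.09 with the ratio. With ρ = 0 the range is 0.04 to 0.18. The ratio is then significant in 21% of studies (about 8% to 64%), against 97% when MPV is analysed directly. Letting ρ vary from −0.4 to +0.4 widens the correlation to −0.08 to 0.23.

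**Step 5: levels against changes.** Assume a baseline count log-SD of 0.25, an independent change of 0.15 and an MPV log-SD of 0.10. The T2 count log-SD is √(0.25² + 0.15²) = 0.292. A marker at 0.5 with the change has 0.5 × 0.15 / 0.292 = 0.26 with the T2 count and 0.24 with the ratio. The share carried (0.946) is as before, but the primary result does not fix the size of the level correlations.

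**The case against.** The strongest reply is that no sentence in the protocol is false. It nowhere claims that the ratio is independent of count. The Synopsis objective can be read as letting the ratio cover count and function together, with FACS as the function-specific measure. Section 7 specifies a hypothesis test only for the primary endpoint; secondary parameters are summarised descriptively and relationships are explored. The significance rates above therefore describe tests that the protocol does not prescribe. All spreads are assumed, and adjustment for count is the kind of detail an analysis plan may hold.

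Much of this stands and limits the weight of the point. The rates illustrate how easily a count signal would surface in the ratio; they are not error rates of a planned test. The dilution of an MPV signal is of undetermined size: in the central case the ratio shows 0.19 at ρ = −0.4 and −0.02 at ρ = +0.4, although every grid cell falls below 0.3. Whether MPV/PTC is an accepted activation marker cannot be settled from this protocol.

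What remains is the label. Section 2.2 and the Synopsis endpoint line put the ratio under platelet function without qualification, and Section 3.5 does not. Explorative status does not prevent a ratio correlation from being reported as a function result.

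**Conclusion.** The concern holds. As labelled, MPV/PTC cannot separate the platelet activation from the platelet loss that Section 1.2 hypothesises, and the sections disagree on whether it is a function measure. More than half of a count-only correlation reaches the ratio under every range tried: 95% in the central case, 71-99% over the grid, and 59% at the lowest point of the wider range. This rests on assumed spreads and on a marker related to the count at the same time point and not separately to MPV.

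The scope is limited. The primary endpoint, the "correlation of the change of C5b-9 and change of platelet count from baseline (T0") to T2, does not involve the ratio. FACS does not have count as its denominator. The change is a worthwhile improvement to secondary, explorative analyses and does not affect the validity of the main result.

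**What to change.** 1. Base conclusions about platelet function on FACS, as Section 3.5 already does, and analyse MPV as a variable separate from count.
2. If MPV/PTC is kept for comparison with the cited study, describe it as count-dependent. Report its Spearman correlation beside that of platelet count, and add the partial Spearman correlation given count at the same time point.
3. Align the Synopsis, Section 2.2 and Section 3.5 on the status of the ratio.

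The cost is wording in three places and one extra explorative analysis. Count, MPV and FACS are already in the T0-T8 samples, so no new blood is needed. The downside is a slightly longer analysis, and the ratio adjusted for count will mostly reflect MPV.

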3. INVESTIGATIONAL PLAN

3.1. General Design of the Study

This is a prospective observational single center study in elective cardiac surgery patients undergoing coronary artery bypass grafts **with or without valve surgery (max. 2 valves) and elective valve surgery (max. 2 valves)**.

Patient care is not influenced by the study and follows clinical routine. Patient follow up will be until hospital discharge or day 30 after surgery.

3.2. Timetable

- T0 baseline: after insertion of arterial cannula beginning surgery
- T1 after re-opening aortic clamp on CPB
- T2 15 minutes after protamine infusion
- T3 end of surgery = admission lab at the postoperative intensive care unit
- T4 4 hours after surgery/admission
- T5 12 hours after surgery/admission
- T6 24 hours after surgery begin
- T7 48 hours after surgery begin
- T8 72 hours after surgery begin
- T9 30 days after surgery or hospital admission

3.3. Blood sampling

3.3.1 Study related blood samples (T0-T8)

- Levels of complement factors: c5-b9, C1q (C1r/C1s), C3a, C5a, MBL, Factor B, Factor D
- mtDNA (human NADH dehydrogenase 1 gene)
- Platelet count, mean platelet volume, fluorescence-activated cell sorting (FACS)
- Coagulation factors: FI – FXIII, FXa, FXIIa, Kallikrein, Bradykinin, endogenous thrombin potential (ETP)
- Residual plasma and serum from blood samples will be stored at -80°C for further differentiated complement and mtDNA assays if useful

3.3.2. Collection of routinely measured laboratory parameters, and clinical data (T0-T9)

The following routine laboratory parameters will be collected if available:

activated clotting time (ACT), Rotem parameters, Multiplate test analysis, whole blood cell count, standard plasmatic coagulation tests, blood gas analysis, CRP, Procalcitonin (PCT), renal and liver function parameters, cardiac enzymes (CK, CK-MB, Myoglobin, Trop T, NTpro BNP)

Study related blood sampling will overlap with routine blood sampling.

Clinical Data

The following parameters will be collected at baseline(T0):

age, gender, body weight(kg) and size (cm), medical history (chronic renal impairment, Diabetes, Hypertension, previous myocardial infarction, previous stroke, previous percutaneous coronary intervention, previous CABG), pre-medication, Euroscore II.

During surgery following data will be collected if available:

Details on CPB, Cell Saver blood volume, blood pressure (BP), hear rate (HR), central venous pressure (CVP), mean pulmonary artery pressure (MPAP), cardiac index (C.I.), cardiac output (C.O.), Oxygen Saturation (SpO2), Horowitz, Fraction of inspired Oxygen (FiO2), Diuresis per hour, Concomitant Medication, transfusion and coagulation products, , need for extracorporeal membrane oxygenation (ECMO), need for inhalative NO

As appropriate, the above mentioned clinical data will be collected until POD3 (T1-T9).

